13.4 Data retention

The investigator maintains all clinical investigation records for the minimum time required in the country in which the clinical investigation is conducted (Australia). Records to be retained may include: all correspondence, documentation of device receipt and disposition, each subject's case history and record of exposure to the device, the clinical investigation plan and amendments, Investigator Brochure, and dates and reasons for any deviations to the clinical investigation plan or as otherwise specified by the applicable laws and regulations.

Furthermore, the documentation will be kept by JiffyStent Pty Ltd for a period of at least 15 years after the clinical investigation with the device in question has ended, or, if the device is subsequently placed on the market, at least 10 years after the last device has been placed on the market.

13.5 Data variables collected

Data collection will include:

13.5.1 Participant demographics

- Participant unique identifier number (UIN)
- Age (years)
- Sex (Male/Female)
- Indication for stent insertion
- Stone characteristics
 - Size (in mm)
 - Position (Proximal/Mid/Distal ureter)
 - Estimated length of participant's ureter from imaging (in cms)
- Past Urological History including Past stent insertions (& ease), past stones and previous procedures (collected via medical history review and participant assessment).

13.5.2 Procedure Information

- Device serial number
- Duration of procedure (mins:secs) including:
 - Set-up time (opening sterile JSI packaging to the connection of the sterile saline IV to JSI)
 - Instrumentation time (time from insertion to removal of JSI)
- Environment procedure performed in
- Equipment utilised
- Guidewire setting length

13.5.3 Investigator Experience

- Rate each of the following (1-5) upon ease of
 - Opening of sterile package
 - Setting of estimated ureter length on guidewire spool using adjustable pin
 - Loading of ureteric stent onto guidewire and into ready position (including use of provided pusher)
 - Winding action of guidewire spool
 - Connection of JSI to Smart device utilising QR codes
 - Visual/connection quality of Smart device video feed
 - Connection of irrigation fluids
 - Ergonomics of JSI insertion into urethra
 - Insertion of JSI into urethra
 - Aligning guidewire with desired ureteric orifice
 - Advancement of guidewire & stent along ureter to desired position
 - Ability to maintain visualisation of ureteric orifice during GW advancement & retraction
 - Disconnection of stent
 - Removal of JSI from urethra

- Analgesia/sedation utilised.
- Perceived participant tolerance of procedure (very poorly, poorly, tolerated, well tolerated)
- Difficulties encountered.
- Complications
- Overall rating of JSI procedure
- Other comments

13.5.4 *Participant experience*

- Measurement of pain before during and after treatment
- Rate of experience and satisfaction
- Other comments

13.6 Source data requirements

The investigator or its delegate will perform primary data collection drawn from original documents (printed, optical or electronic document containing source data). Data to be collected for purposes of the clinical investigation must not be entered directly into the eCRF before being recorded first in the source documents. All source documentation must be available for review by the study monitor during monitor visits. Source data is defined as all information in original records, certified copies of original records of clinical findings, observations, or other activities in a clinical investigation, necessary for the reconstruction and evaluation of the clinical investigation. This includes source data initially recorded in an electronic format.

13.7 Data quality and monitoring

Several procedures to ensure data quality and protocol standardisation will help to minimise bias and to optimise data quality. These include:

- Study design
- Use of specific inclusion and exclusion criteria
- A site initiation training will be conducted before the start of the trial to ensure consistency in procedures.
- A detailed data dictionary will define the data to be collected and entered into the eCRF
- The management committee will perform timely validation of data entered into the eCRF, queries and corrections.

The sponsor will use a combination of monitoring techniques: central, remote, or on-site monitoring, to monitor this study. The sponsor will perform on site monitoring visits as frequently as necessary. The monitor will record dates of the visit in a study visit log that will be kept at the study site stop direct access to source documents (medical records) must be allowed for the purpose of verifying that the recorded data are consistent with the original source data.

Findings from this review will be discussed with the study site personnel. The sponsor expects that, during monitoring visits, the relevant study site personnel will be available, the source documents will be accessible, and a suitable environment will be provided for review of study related documents. The monitor will meet with the investigator on a regular basis during the study to provide feedback on the study conduct.

14 STATISTICAL CONSIDERATIONS

14.1 Power calculation and sample size

This is a first-in-human, proof-of-principle pilot study to determine feasibility of a human trial therefore, analysis of the study endpoints will be done using descriptive statistics. Descriptive statistical variables will include the mean (with two-sided 95% confidence intervals), standard deviation, median, minimum, and maximum for continuous variables and frequency and percentage (with two-sided exact 97% confidence intervals) for categorical variables. Descriptive tables will be produced for baseline characteristics including demographics and medical history, procedure, adverse events, medications, physical exams, protocol deviations and outcomes. The study has an exploratory nature and, as such, no formal sample size estimation has been performed. A sample size of 5-15 participants is expected to provide meaningful data for future design and development considerations.

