 - Measure: Investigators will receive a User Questionnaire regarding their experience of using the JSI. Collated data will be analysed 3-6 months post-intervention commencement.
- Impact on workflow data
 - Measure: Analysis of improvements in workflow including time in the ED-SSU, total length of stay, time utilisation by urology doctors.
 - Timepoint: At follow up visit for definitive stone management surgery (within 14-21 days)
- Impact on health economics
 - Measure: Comparison of costings related to length of stay, admission, operating room utilisation, staffing, equipment.
 - Timepoint: At study completion. A health economist will be engaged to help perform the analysis.

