17 DEVICE ACCOUNTABILITY

Access to investigational devices will be controlled and the investigational devices will be used only in the clinical investigation and according to the clinical investigation plan. The sponsor will keep records to document the physical location of all investigational devices from shipment of investigational devices to the investigation sites until return or disposal. The sponsor shall have instructions in place and make packaging materials available, if applicable, for the safe return or disposal of investigational devices, including potentially hazardous devices.

The principal investigator or an authorised designee shall keep records documenting the receipt, use, return and disposal of the investigational devices, which shall include:

- a) name(s) of person(s) who received, used, returned or disposed the device,
- b) the date of the receipt,
- c) identification of each investigational device (batch number/serial number or unique code),
- d) quantity of investigational devices,
- e) the expiry date, if applicable,
- f) the date or dates of use,
- g) subject identification,
- h) date on which the investigational device was returned/explanted from subject, if applicable,
- i) the date of return of unused, expired or malfunctioning investigational devices, if applicable.
- j) the date and documentation of disposal of the investigational devices as per instructions of the sponsor, if applicable.

Written procedures will be established for the entire process of device accountability.

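### Section 14.1's interval rule, applied to doctor ratings given once per procedure, takes no account of the same doctor rating several procedures, and the listed data variables do not include the operator

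*Protocol*

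**What the plan says.** Section 14.1 covers the analysis of the study endpoints with one sentence. Continuous variables get the "mean (with two-sided 95% confidence intervals), standard deviation, median, minimum, and maximum for continuous variables"; categorical variables get "frequency and percentage (with two-sided exact 97% confidence intervals) for categorical variables". It describes the study as exploratory, says that "no formal sample size estimation has been performed", and adds: "A sample size of 5-15 participants is expected to provide meaningful data for future design and development considerations".

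Section 8.3.2 lists user satisfaction and mechanical reliability as secondary endpoints, and section 14.4 repeats them. For user satisfaction, "Investigators will receive a User Questionnaire regarding their experience of using the JSI". Reliability is the treating doctor's rating on a global satisfaction score. The schedule in section 9.2 (note d) places the user questionnaire directly after the insertion, so there is one set of ratings per procedure. The items in section 13.5.3 open with "Rate each of the following (1-5) upon ease of".

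Section 9.1 gives one centre and up to 15 participants. Section 6.7 limits use of the device to clinicians trained by the sponsor. No section gives the number of operators.

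Section 13.5.2 lists procedure data such as the device serial number and "Environment procedure performed in", but not who operated. That is kept in the device accountability record of section 17, which holds the "name(s) of person(s) who received, used, returned or disposed the device".

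**The concern.** The ordinary t interval and the exact binomial interval both assume independent observations. It therefore makes no difference to this point whether the 1-5 ratings are treated as continuous or categorical. Several questionnaires from one doctor share that doctor's habits, skill and leniency. Pooling them over procedures counts procedures where a statement about users needs to count users. In the extreme case of one doctor doing all 15 procedures, the data hold one user's opinion expressed 15 times.

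What is at stake is a misleading summary. These ratings are meant to inform further design and development, and an interval that looks precise could be read as showing how urological users in general would rate the device. The protocol itself regards the operator as a source of variation: section 9.12 lists misuse by the investigator as a potential confounder, and section 11.2.1 gives inexperience of the user as one reason for not seeing the ureteric orifice. The listed data variables nevertheless leave the operator out.

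**Working it through.** The protocol gives no interval width, operator count or correlation for these ratings, so there is no figure to reproduce.

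**Inputs from the protocol.** n = 5 to 15 procedures (14.1; up to 15 in 9.1); nominal level 95% for means (14.1); one questionnaire per procedure (9.2).

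**Assumed inputs.** Number of operators k = 1, 2, 3, 5, or one per procedure; ICC 0 to 0.5; procedures split as evenly as possible; normally distributed ratings. Section 7.3 confirms that there are no prior clinical data to narrow these.

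**Interval without allowance for operators.** Half-width = t(0.975, n-1) × SD/√n. At n = 15 this is 0.55 SD; at n = 10, 0.72 SD; at n = 5, 1.24 SD.

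**Effect of repeated raters.** Design effect DEFF = 1 + (Σm_j²/n − 1) × ICC, where m_j is the number of procedures by operator j. The standard error is understated by √DEFF, and the effective sample is n/DEFF. At n = 15:

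- k = 2, split 8 and 7, ICC 0.5: Σm_j²/n = (64 + 49)/15 = 7.53. DEFF = 1 + 6.53 × 0.5 = 4.27, √DEFF = 2.07, effective n = 15/4.27 = 3.5.
- k = 3, ICC 0.1: Σm_j²/n = 75/15 = 5. DEFF = 1 + 4 × 0.1 = 1.40, √DEFF = 1.18, effective n = 10.7.
- k = 1, ICC 0.5: Σm_j²/n = 225/15 = 15. DEFF = 1 + 14 × 0.5 = 8.00, √DEFF = 2.83, effective n = 1.9.

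**Coverage.** A random-intercept model with 100,000 simulated studies per cell gives the true coverage, for the mean over users, of the nominal 95% t interval at n = 15 (√DEFF in brackets):

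| Operators | ICC 0.1 | ICC 0.3 | ICC 0.5 |
|---|---|---|---|
| 1 | 79% (1.55) | 56% (2.28) | 40% (2.83) |
| 2 | 87% (1.29) | 73% (1.72) | 61% (2.07) |
| 3 | 90% (1.18) | 81% (1.48) | 71% (1.73) |
| 5 | 93% (1.10) | 88% (1.26) | 82% (1.41) |
| 15 (one each) | 95% (1.00) | 95% (1.00) | 95% (1.00) |

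With ICC 0, coverage is 95% for any number of operators. With only 5 procedures the effect is smaller: √DEFF runs from 1.0 to 1.7 and coverage from 95% to 68%. The simulation was run for the t interval only. The exact interval for percentages rests on the same independence assumption, but its coverage was not computed.

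**Would an interval that allows for operators help?** Using t(0.975, k−1) × √(DEFF/n) at n = 15 and ICC 0.5, the half-width is 12.71 × √(4.27/15) = 6.78 SD for k = 2 and 4.30 × √(3.00/15) = 1.92 SD for k = 3. For k = 1 no such interval exists. With few operators, a listing is more informative than any interval.

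**The case against.** The case on the other side has real weight.

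- **Section 14.1 is generic.** It names neither user satisfaction nor reliability, does not say that procedures count as independent users, and leaves open whether a 1-5 score is continuous or categorical. This stands as a description. Still, the rule is stated for the study endpoints, these are named endpoints, and either branch ignores the operator.
- **The SAP may deal with it.** Section 14.6 refers to one that is not shown, and it could set another summary. It would need an operator variable, however, and the protocol's list of data does not contain one. The data dictionary mentioned in section 13.7 might add it.
- **The operator can be recovered.** This stands. Section 17 records user, device, date and participant, section 13.5.2 holds the serial number, and the enrolment log in section 10.5 holds date and time. A reader might infer that operator effects are lost from the data. They are not, but no section plans the linkage.
- **The procedure may be the right unit.** Each procedure uses a new single-use device (6.8, 6.9), so for mechanical reliability a count per device is defensible. Several 13.5.3 items also rate events within one procedure. This stands. The coverage figures concern generalising to users, which the protocol does not expressly claim.
- **The size is assumed.** This stands. A reader might infer that the interval must be far too narrow, but operator count and ICC are not in the protocol, and the loss of coverage runs from nil to severe.
- **Recording case order does not separate learning from setting.** This also stands. Section 15.8 places the five operating-room cases before further enrolment, so early cases and operating-room cases coincide.

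**Conclusion.** The point holds conditionally. Followed as written, section 14.1 gives an interval on doctor ratings that is too narrow as a statement about users whenever doctors rate more than one procedure and their ratings are positively correlated. Repeat rating is likely at one centre with a restricted group of trained operators, but it is not stated.

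The consequence ranges from none (a different operator each time), through minor (standard error understated by a factor of about 1.1 to 1.2 with 3-5 operators and ICC 0.1), to a standard error understated twofold or more (1 or 2 operators and ICC 0.5). All of these figures rest on assumed operator counts and correlations.

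It might also be inferred that a go/no-go decision for the pivotal trial would be distorted. The protocol does not support that: the endpoints are secondary and descriptive, with no test, threshold or decision rule attached to the ratings. This is an inexpensive improvement to reporting.

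**What to change.** 1. In section 13.5.2, add an operator code and that operator's running JSI case number.
2. In sections 14.1 and 14.4, state that the 13.5.3 user ratings and the doctor's reliability rating are reported with the number of operators and the number of ratings per operator, by operator and in case order, without a confidence interval pooled over procedures.
3. List placement success and insertion time by operator and case order too. This makes a learning effect visible; it does not separate learning from setting, and the report should say so.

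The cost is two eCRF fields, both available or derivable from records already kept under section 17, and a sentence of analysis text. Trial conduct does not change. The fields are easiest to add before enrolment starts. The downside is that the user ratings lose a pooled interval.

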14.2 Statistical Design & Methods

This study has a single arm design in which all participants followed will have received a JiffyStent Inserter treatment. Participants will be unblinded to their treatment, and no participants will be randomised to a parallel group receiving a control treatment.

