8.2 Hypothesis

That the JiffyStent Inserter can reliably, safely, quickly, effectively and to the participant's and doctor's satisfaction, insert a ureteric stent into the ureter of a participant with renal colic.

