9 OVERALL STUDY DESIGN

9.1 Study design

Single centre, first-in-human pilot study of a novel medical device. The study will involve two groups up to 15 participants under controlled conditions. Of the 15 total participants, five (5) will be individuals who require a stent as a standard part of their urological procedure (Group 1) and 5-10 participants will be individuals who present to the ED-SSU with acute renal colic from a kidney stone and require a ureteric stent insertion (Group 2).

- Participants requiring a stent as part of standard urological procedure will be placed under general anaesthetic

in the operating room as per standard of care. The ureteric stent will then be inserted using the JSI under standard controlled conditions.

- In participants who present to the emergency room, a stent will be inserted in the ED-SSU cubicle using the JSI by an experienced urological doctor who is skilled in inserting ureteric stents. Analgesia for the procedure will include the local topical anaesthetic gel (i.e. Instillagel®) injected into the urethra prior to device insertion and a Pentrox “green whistle” temporary inhaled anaesthetic. A post-stent insertion KUB X-ray will then be performed to confirm position of the stent.

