14.5 Analysis Populations

Analysis of the primary objective will be conducted using the intent-to-treat sample including all participants treated with the JSI.

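### The primary analysis pools operating-room and emergency-unit participants, so its success rate does not isolate the renal colic population named in the hypothesis

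*Protocol*

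**What the plan says.** Section 9.1 of the protocol sets up two groups: "The study will involve two groups up to 15 participants under controlled conditions".

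- **Group 1** is five people who need a stent as part of a urological procedure; renal colic is not required. "Participants requiring a stent as part of standard urological procedure will be placed under general anaesthetic", in the operating room.
- **Group 2** is described as follows: "5-10 participants will be individuals who present to the ED-SSU with acute renal colic from a kidney stone". For them, "a stent will be inserted in the ED-SSU cubicle using the JSI by an experienced urological doctor", with topical anaesthetic gel and an inhaled agent. No general anaesthetic is planned.

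The hypothesis in Section 8.2 is that the device can "insert a ureteric stent into the ureter of a participant with renal colic". Section 11.1 claims, among other benefits, insertion without an operating theatre and without general anaesthetic.

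Section 14 does not use the groups. Section 14.2 says: "This study has a single arm design in which all participants followed will have received a JiffyStent Inserter treatment". Section 14.5 says: "Analysis of the primary objective will be conducted using the intent-to-treat sample including all participants treated with the JSI". Sections 14.3 and 14.4 name the endpoints without saying how they are to be summarised by group. Section 14.1 makes the analysis descriptive, with exact 97% intervals for categorical variables and no formal sample size.

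**The concern.** The two groups differ in indication, setting and anaesthesia, and only Group 2 matches the hypothesis. By design, Group 1 uses both the theatre and the general anaesthetic that the device is meant to avoid, so it cannot show those benefits, yet it contributes to the one primary proportion. That proportion is a weighted average of two success rates, and its value depends partly on how many Group 2 participants happen to be enrolled.

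Group is also tied to order of use, because the operating-room participants are treated first (Sections 5.1 and 15.8). A difference between the groups could therefore come from the setting, the indication or growing experience with the device, and it could run in either direction. A single pooled figure would show none of this.

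The synopsis and Section 5.1 say that a positive outcome will lead to a pivotal trial. A pooled rate read as the rate in renal colic could carry a wrong planning value into that trial.

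Two of the secondary measurements also do not carry over between groups: pain during the procedure has no useful meaning under general anaesthetic, and time in the ED-SSU is not part of the pathway described for Group 1.

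**Working it through.** **Inputs.** Group 1 has 5 participants and Group 2 has n2 = 5 to 10 (Section 9.1). The interval for a proportion is two-sided exact at 97% (Section 14.1). The only expected failure figure is 5-10%, given once for all participants (Section 10.4). The protocol gives no success rates by group, so those used below (p1 for Group 1, p2 for Group 2) are assumptions.

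**Sample size.** 5 + 10 = 15 reproduces the stated maximum. The minimum implied by Section 9.1 is 5 + 5 = 10. Section 14.1 speaks of 5-15, but a total of 5 would leave no Group 2 participant once Group 1 is filled, so 10-15 is used here.

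**Weight of Group 1 in the pooled rate.** w = 5 / (5 + n2).

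- n2 = 10: 5/15 = 33%
- n2 = 5: 5/10 = 50%

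**Gap between the pooled rate and the Group 2 rate.** Pooled rate = (5 × p1 + n2 × p2) / (5 + n2), so pooled rate − p2 = w × (p1 − p2).

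| Assumed p1, p2 | Gap, n2 = 10 | Gap, n2 = 5 |
|---|---|---|
| 90%, 90% | 0 | 0 |
| 95%, 90% | 5/3 = 1.7 points | 5/2 = 2.5 points |
| 95%, 70% | 25/3 = 8.3 points | 25/2 = 12.5 points |

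The second row spans the protocol's own 5-10% failure range. The third goes beyond it and shows what would happen if the device did markedly worse in the cubicle. If p1 were below p2, the sign would reverse.

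**One possible result.** Group 1 succeeds in 5/5 and Group 2 in 8/10. The pooled figure is 13/15 = 86.7% (exact 97% interval 56.8% to 98.7%); Group 2 alone is 80.0% (41.2% to 98.1%).

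**Precision if Group 2 is the headline.** With no failures, the exact (Clopper-Pearson) 97% lower limit is 0.015^(1/n).

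| n | Lower limit |
|---|---|
| 5 | 43.2% |
| 10 | 65.7% |
| 15 | 75.6% |

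With ten Group 2 participants, the lower limit falls from 75.6% (15 pooled) to 65.7%. With five, it falls from 65.7% (10 pooled) to 43.2%.

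**The case against.** The strongest defence is that this is a small descriptive study with no test, power calculation or success threshold, so no stated decision turns on the pooled rate. The all-treated population also fits other parts of the protocol: the primary endpoint in 8.3.1 refers to a suitable participant, the aim in 8.1 names no indication, and the intended population in 6.6 includes routine stenting. Indication, procedure environment and analgesia are recorded for each participant (13.5.1 to 13.5.3), so 10-15 records can easily be split. The safety committee reviews the five operating-room participants before further enrolment (15.8). Section 14.6 refers to a SAP, which is not shown and may add tables by group.

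Much of this limits the point without removing it. Section 14.5 itself fixes the pooled population for the primary objective. A SAP may add tables by group, but the pooled rate would still be the primary result. The safety committee's review governs continuation, not the final reporting.

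Four stronger readings are tempting, and the documents do not support them:

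- **That Section 14.2 prescribes the pooling.** Its next sentence concerns the absence of a randomised control, and that is all the single-arm label means.
- **That the trial cannot answer its hypothesis.** Renal colic participants make up 50-67% of the planned sample and their data can be read separately, though with low precision.
- **That pain, satisfaction, workflow and cost will be reported as pooled means.** No section plans this: 14.4 only lists endpoints and 14.5 covers only the primary objective. Items that do not apply are marked as such (13.3) and outcomes are not imputed (14.8), so pain during anaesthesia would not enter a mean as zero.
- **That Group 2 is simply awake.** The protocol does not use the word, and 11.2.1 lists intravenous sedatives and analgesics as further options.

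**Conclusion.** The point holds for the primary endpoint. As written, the primary success rate mixes two populations, and one third to one half of its denominator comes from an indication, setting and anaesthesia other than those in the hypothesis and the claimed benefits. It does not isolate performance in renal colic.

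The size cannot be known from the protocol. It is zero if the groups perform alike, 1.7-2.5 points if the true rates are 95% and 90%, and 8.3-12.5 points if they are 95% and 70%. The direction assumes that the operating room is the easier setting, for which the protocol gives no figure.

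For the secondary endpoints the point is narrower. The protocol does not plan pooled summaries of them, but it does not say that they will be shown by group either, and two measurements are informative only in Group 2. The change is worth making because the groups are already defined, the data are already collected and the study is meant to inform a pivotal trial.

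**What to change.** In Sections 14.3 to 14.5:

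1. Report the primary endpoint and the secondary endpoints separately for Group 1 and Group 2, with exact intervals for proportions at whichever confidence level the protocol settles on (Section 14.1 currently gives 97% for categorical variables and 95% for means).
2. Name the Group 2 success proportion as the estimate that addresses Section 8.2.
3. Keep the proportion in all treated participants as a supportive figure.
4. Summarise pain during the procedure and time in the ED-SSU for Group 2 only.
5. Keep all other questionnaire, length-of-stay, workflow and cost data for both groups, shown by group. The 14-21 day questionnaire is usable in Group 1, and the participant questionnaire is one of the stated safety measures in 8.3.2, so dropping it for the first five people treated would lose information.

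The cost is a few sentences and extra table columns, with no new data and no more participants. The real downside is the wider interval for the headline estimate. That width is the actual precision available for renal colic, and including Group 1 narrows the interval only by changing the question.
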